8.5. Electrocardiograms

Twelve-lead ECGs including PR, QRS, QT, QTcB, QTcF, and RR intervals will be obtained for each participant during the study. Change and percentage change from baseline will be calculated at each postbaseline assessment time. Descriptive statistics will be determined for each ECG parameter.

Incidences of clinically notable ECG abnormalities are defined in [Table 3](#). Participants exhibiting clinically notable ECG abnormalities will be listed with study visit. Abnormal values for participants with alert ECG values, defined as an absolute value outside the defined normal ranges and the percentage change from baseline outside (-25%,25%), will be identified and listed.

When triple ECGs are measured, the average of the 3 ECGs will be used in the summary table, but all 3 of these ECGs will be listed.

Table 3: Criteria for Clinically Notable Electrocardiogram Abnormalities

Parameter	High Threshold	Low Threshold
QTcF	> 460 msec	< 295 msec
QTcB	> 460 msec	< 295 msec
PR	> 220 msec	< 75 msec
QRS	> 120 msec	< 50 msec
QT	> 500 msec	< 300 msec
RR	> 1330 msec	< 600 msec

QTcF = Fridericia correction.

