8.3.4. Electrocardiograms

Single 12-lead ECGs will be obtained as outlined in the SoA (see [Table 3](#)) using an ECG machine that automatically calculates the heart rate and measures PR, QRS, QT, and QTc intervals. All 12-lead ECGs will be performed as indicated in [Table 9](#) with the participant in a recumbent or semirecumbent position after 5 minutes of rest.

The 12-lead ECGs will be interpreted by the investigator at the site to be used for immediate participant management and care. Additional 12-lead ECGs may be performed as clinically indicated to manage participant safety. The decision to include or exclude a participant or withdraw a participant from the study treatment based on an ECG flagged as "Abnormal, Clinically Significant" is the responsibility of the investigator, in consultation with the sponsor's medical monitor, as appropriate. Clinically notable abnormalities that are considered clinically significant in the judgment of the investigator are to be reported as AEs.

Table 9: Electrocardiogram Schedule

Study Visit	Timing of Electrocardiogram Relative to Administration of Study Drug		
	Not Applicable	Predose (Trough) ECG	Postdose ECG
Screening ^a	Single → Triple ^b		
Day 1 ^c		Triple	Single → Triple ^b
Week 2 ^c		Single → Triple ^b	Single → Triple ^b
Week 12 ^d			Single → Triple ^b

^a Prolonged QTcF values (> 470 milliseconds for males or > 480 milliseconds for females) at screening are to be confirmed by performing 2 additional ECGs and averaging the results to determine whether the averaged value meets the exclusion criterion.

^b Single → Triple: Single ECG will be performed first. If prolonged QTcF intervals (defined as > 470 milliseconds for males or > 480 milliseconds for females) are observed, an additional 2 ECGs will be measured within the next 5 minutes.

^c Day 1 and Week 2 postdose ECGs will be performed after participants complete all of the study assessments [REDACTED]

^d Week 12 postdose ECGs will be performed after participants complete all of the study assessments.

All ECG measurements should be performed before blood draws for laboratory [REDACTED] assessments, and all predose (trough) ECG measurements should be taken before the participant takes study drug for that day.

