8.4. Vital Signs

Values at each scheduled visit, change, and percentage change from baseline for vital signs, including systolic blood pressure, diastolic blood pressure, pulse, respiratory rate, and body temperature will be summarized descriptively.

Criteria for clinically notable vital sign abnormalities are defined in [Table 2](#). The abnormal values for participants exhibiting clinically notable vital sign abnormalities will be listed. Alert vital signs are defined as an absolute value outside the defined range and percentage change from baseline outside (-25%, 25%). The abnormal values for participants exhibiting alert vital sign abnormalities will be listed.

Table 2: Criteria for Clinically Notable Vital Sign Abnormalities

Parameter	High Threshold	Low Threshold
Systolic blood pressure	> 155 mmHg	< 85 mmHg
Diastolic blood pressure	> 100 mmHg	< 40 mmHg
Pulse	> 100 bpm	< 45 bpm
Respiratory rate	> 24 breaths/min	< 8 breaths/min
Temperature	> 38°C	< 35.5°C

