3.5 ECG		
3.5.1	Summary of PR Interval (msec) From 12-Lead ECG	FAS
3.5.2	Summary of RR Interval (msec) From 12-Lead ECG	FAS
3.5.3	Summary of QT Interval (msec) From 12-Lead ECG	FAS
3.5.4	Summary of QRS Interval (msec) From 12-Lead ECG	FAS
3.5.5	Summary of QTcB Interval (msec) From 12-Lead ECG	FAS
3.5.6	Summary of QTcF Interval (msec) From 12-Lead ECG	FAS
3.5.7	Summary of Heart Rate (bpm) From 12-Lead ECG	FAS
3.5.8	Summary of Outliers of QT, QTcB, and QTcF Interval Value (ms) From 12-Lead ECG	FAS
3.5.9	Summary of Clinically Significant ECG Abnormality	FAS

Listings

Listing No.	Title
Demographic and Baseline Characteristics	
2.1.1	Participant Enrollment and Disposition Status
2.1.2	Participant Inclusion and Exclusion Criteria Violations
2.2.1	Protocol Deviations
2.4.1	Demographic
2.4.2	Baseline Disease Characteristics
2.4.3	General Medical History
2.4.4	Prior and Concomitant Medications
2.4.5	Prior Medications for Sjögren's syndrome
2.5.1	Study Drug Compliance
Efficacy	
2.6.1	SGUS Score
2.6.2	Stimulated and unstimulated salivary flow
2.6.3	ESSDAI
2.6.4	ESSPRI
2.6.5	Symptom scores for dryness of eyes, mouth, and vagina
2.6.6	PGIC category
2.6.7	PROMIS Fatigue
2.6.8	FSFI
2.6.9	EQ-5D
Adverse Events and Exposure	
2.7.1	Study Drug Administration
2.7.2	Adverse Events
2.7.3	Serious Adverse Events
2.7.4	Grade 3 and Higher Adverse Events
2.7.5	Adverse Events Leading to Death
2.7.6	Treatment-Related Adverse Events
2.7.8	Adverse Events Leading to Dose Interruption
2.7.9	Adverse Events Leading to Discontinuation

Listing No.	Title
Laboratory Data	
2.8.1	Clinical Laboratory Values – Hematology
2.8.2	Clinical Laboratory Values – Serum Chemistry
2.8.3	Abnormal Clinical Laboratory Values – Hematology
2.8.4	Abnormal Clinical Laboratory Values – Serum Chemistry
Vital Signs	
2.9.1	Vital Signs
2.9.2	Abnormal Vital Sign Values
2.9.3	Alert Vital Sign Values
ECG	
2.10.1	12-Lead ECG Values
2.10.2	Abnormal 12-Lead ECG Values
2.10.3	Alert 12-Lead ECG Values

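### SAP 8.5's alert ECG rule needs a change of 25% or more from baseline, which for QTcF and QTcB means a rise of at least 92 ms, so it will almost never flag QTc prolongation

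*SAP*

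**What the plan says.** SAP 8.5 (Electrocardiograms) sets up two tiers of individual ECG reporting.

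- **Clinically notable.** A value beyond a Table 3 limit, with no change condition: QTcF or QTcB above 460 msec, QT above 500 msec, plus limits for PR, QRS and RR. "Participants exhibiting clinically notable ECG abnormalities will be listed with study visit". Appendix A plans Listing 2.10.2, "Abnormal 12-Lead ECG Values".
- **Alert.** A value "defined as an absolute value outside the defined normal ranges and the percentage change from baseline outside (-25%,25" percent. The two conditions are joined by *and*, and one percentage serves all parameters. Appendix A plans Listing 2.10.3, "Alert 12-Lead ECG Values".

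SAP 8.4 uses the same percentage for vital signs: "Alert vital signs are defined as an absolute value outside the defined range and percentage change from baseline outside (-25%, 25" percent. The SAP gives no ECG-specific reason for it.

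Appendix A also plans Listing 2.10.1 (all 12-lead ECG values), summary tables by parameter, and Table 3.5.8, "Summary of Outliers of QT, QTcB, and QTcF Interval Value (ms) From 12-Lead ECG". The SAP text gives no cut-offs for Table 3.5.8, and the shells are in a separate document.

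Protocol 8.3.4, Table 9, footnote b, sets its own marker of prolongation, on absolute value only, as the trigger for repeat ECGs: "If prolonged QTcF intervals (defined as > 470 milliseconds for males or > 480 milliseconds for females) are observed".

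**The concern.** A 25% relative change is a very different demand for different ECG intervals. QTc values are several hundred milliseconds, so 25% of baseline is around 100 ms. A rule that waits for that much movement does little to mark out participants whose QTc has lengthened.

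ECG results are a named part of the safety endpoint, and the study has one arm. Within-participant change is therefore the main evidence on a QT effect. The notable tier looks only at the value reached: it treats 455 to 461 ms and 380 to 461 ms the same. The alert tier is the only rule in the readable SAP that flags an individual ECG on change, so its usefulness for QT and QTc matters.

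**Working it through.** **Inputs from the documents.** High limits from SAP Table 3: QTcF and QTcB > 460, QT > 500, PR > 220, QRS > 120; low limit for RR < 600 (all msec). Change condition: 25% or more in either direction, since a value of exactly 25% lies outside the open interval. I read the *defined normal ranges* as the Table 3 limits; the SAP does not say so expressly, but no other ranges are given.

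**Assumption.** The documents give no baseline QT or QTc, so I use 360 to 450 ms. The SAP states no millisecond figure for the alert rule, so there is none to reproduce.

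**Rise needed for a high-side alert.** Value needed = max(Table 3 limit, 1.25 × baseline); rise = value needed − baseline.

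| Baseline (ms) | QTcF/QTcB value | Rise | QT value | Rise |
|---|---|---|---|---|
| 360 | 460 | 100 | 500 | 140 |
| 368 | 460 | 92 | 500 | 132 |
| 380 | 475 | 95 | 500 | 120 |
| 400 | 500 | 100 | 500 | 100 |
| 420 | 525 | 105 | 525 | 105 |
| 450 | 562.5 | 112.5 | 562.5 | 112.5 |

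The minimum falls where the two conditions meet: 460/1.25 = 368 for QTc (rise 92) and 500/1.25 = 400 for QT (rise 100).

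**Familiar sizes of change against the rule.**
- A 60 ms rise is 60/380 = 15.8% to 60/450 = 13.3% of baseline, so it does not qualify.
- QTcF of 500 ms from 420 ms is +19.0%: not an alert.
- 470/1.25 = 376 and 480/1.25 = 384. A man with a baseline above 376 ms, or a woman above 384 ms, can pass the Protocol's prolongation marker without being an alert.
- 380 to 455 ms is +75 ms and 75/380 = 19.7%. It is not above 460, so it is neither notable nor an alert.
- 380 to 480 ms is +26.3% and above 460: an alert. Such alerts are possible from low baselines.

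**Other parameters.** 220/1.25 = 176 (PR), 120/1.25 = 96 (QRS), 600/0.75 = 800 (RR, low side). For baselines of PR up to 176, QRS up to 96 or RR from 800, the Table 3 limit already implies a change of at least 25%, so the percentage adds no obstacle on that side.

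**Illustration of a true +60 ms QTcF shift.** Assumptions: baseline mean 420 ms, between-person SD 20, single-reading SD 12, baseline the mean of 3 readings (Protocol Table 9 has a triple predose ECG on Day 1), one reading at the later visit.

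- Variance of the baseline mean's error: 144/3 = 48. SD of observed change: √(144 + 48) = 13.9 ms.
- Change condition alone: (later value − 1.25 × baseline) has mean 60 − 0.25 × 420 = −45 and variance 0.0625 × 400 + 144 + 1.5625 × 48 = 244, SD 15.6. P(≥ 0) = P(Z ≥ 2.88) ≈ 0.2%.
- Both conditions, by simulation: about 0.17% per participant. Any of 12: 1 − (1 − 0.0017)^12 ≈ 2%. With means of 410 to 430 ms this is about 3% to 1%.
- About 50% of participants show an observed rise above 60 ms. P(value > 460) = P(Z > −20/√(400 + 144)) ≈ 80%.
- Rise above 60 ms but value at or below 460: about 10% to 2% of participants for baseline means of 410 to 430 ms.

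**The case against.** The strongest case against is that other displays already show a QT effect.

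- **Prolonged values are listed.** QTcF above 460 ms is reported by participant and visit with no change condition, and 460 lies below both Protocol markers (470 and 480). Everyone who passes those markers is captured.
- **Every value is listed.** Listing 2.10.1 carries no abnormality condition, and all three readings of a triple are listed. With 12 participants, a move from 380 to 455 ms can be read from it.
- **Change is summarised.** In the illustration the standard error of the mean change is 13.9/√12 = 4 ms, so a 60 ms shift would be plain in the QTcF table. About 10 of 12 participants (80%) would be in the notable listing.
- **The shells are unseen.** Table 3.5.8 may already hold change categories.
- **Participants are not affected.** Under Protocol 8.3.4 the investigator reads ECGs on site for immediate care, and repeats depend on absolute QTcF.

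All of this stands, and it limits the consequence. A reader might infer that the alert listing will be empty, or that prolonged QTcF will go unreported. The documents support neither. Listing 2.10.3 can hold PR, QRS and RR alerts and, rarely, QTcF alerts from a low baseline; the notable listing captures QTcF above 460 ms. The 2% describes one listing, not the chance of missing a QT effect.

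What the objection does not remove is that the stated change rule is ineffective for QT and QTc. Finding a large rise that ends at or below 460 ms depends on reading the full listing or noticing a maximum in a summary table. No stated rule identifies the participant. The title of Table 3.5.8 refers to outlying values, and its cut-offs cannot be checked here.

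**Conclusion.** The point holds as a reporting defect of modest consequence. The alert tier needs a rise of at least 92 ms for QTcF and QTcB and at least 100 ms for QT. Those minima follow from the SAP's own limits, read with Table 3 as the normal ranges. The range of 95 to 112.5 ms applies to QTc only and rests on assumed baselines of 380 to 450 ms; for QT the rise from 380 ms is 120 ms. The chance of about 2% for any QTcF alert among 12 at a visit, given a true 60 ms shift, rests on the assumed means and SDs.

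The readable SAP therefore has one individual-level rule based on change, and that rule is uninformative for QT and QTc. A correction is worth making because it is cheap and the data are already there. It bears on how results are displayed, not on participant management or on whether prolonged values are reported.

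**What to change.** In SAP 8.5, keep the 25% condition for PR, QRS and RR. For QT, QTcB and QTcF, replace it with an absolute increase from baseline in milliseconds, not conditional on exceeding the Table 3 limit. Two reporting categories, above 30 ms and above 60 ms, would serve as an example; the documents supply no cut-offs, so the sponsor should choose and state them. Report n (%) in each category in Table 3.5.8, unless the shells already do, and state that table's cut-offs in the SAP text. List the participants in Listing 2.10.3. State also that the defined normal ranges are those of Table 3, if that is meant.

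The cost is a sentence or two in the SAP and minor programming for one listing and one table. No new data are needed, since SAP 8.5 already calculates change from baseline at each assessment. The downside is a few chance flags in the lower category. With no true effect and the SDs above, P(change > 30 ms) = P(Z > 30/13.9) ≈ 1.5% per participant, or 1 − (1 − 0.015)^12 ≈ 17% for at least one of 12 at a visit.

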9. INTERIM ANALYSES

No formal interim analysis is planned in this study.

10. CHANGES AND MODIFICATIONS TO THE ANALYSIS PLAN

All versions of the SAP are listed in [Table 4](#).

Table 4: Statistical Analysis Plan Versions

SAP Version	Date
Original	25 FEB 2019

10.1. Changes to Protocol-Defined Analyses

Not applicable.

10.2. Changes to the Statistical Analysis Plan

Not applicable.

APPENDIX A. PLANNED TABLES AND LISTINGS

This appendix provides a list of the planned tables and listings for the Clinical Study Report. Standard tables will follow the conventions in the Standard Safety Tables initial version. Shells are provided for nonstandard tables in a separate document. In-text tables are identical in structure and content as appendix tables but follow a Rich Text Format.

The list of tables, listings, and the shells are to be used as guideline. Modifications of the list or shells that do not otherwise affect the nature of the analysis will not warrant an amendment to the SAP.

Tables

Table No.	Title	Population
Baseline and Demographic Characteristics		
1.1 Disposition		
1.1.1	Analysis Populations	FAS
1.1.2	Summary of Participant Disposition	FAS
1.1.3	Summary of Number of Participants Enrolled by Site	FAS
1.2 Demography		
1.2.1	Summary of Demographics	FAS
1.3 Baseline Characteristics		
1.3.1	Summary of Baseline Disease Characteristics	FAS
1.4 Prior Medication and Concomitant Medication		
1.4.1	Summary of Prior Medications	FAS
1.4.2	Summary of Prior Medications for Sjögren's Syndrome	FAS
1.4.3	Summary of Concomitant Medications	FAS
1.5 Others		
1.5.1	Summary of General Medical History	FAS
Efficacy		
2.1.1.1	Summary of Participants With 1 Point or Greater Improvement on the SGUS Score at Week 4 and Week 12	FAS
2.1.1.2	Summary of SGUS Score From Baseline to Week 12	FAS
2.1.2	Summary of Stimulated and Unstimulated Whole Salivary Flow From Baseline to Week 12	FAS
2.1.3	Summary of ESSDAI From Baseline to Week 12	FAS
2.1.4	Summary of ESSPRI From Baseline to Week 12	FAS
2.1.5.1	Summary of Symptom Scores for Dryness From Baseline to Week 12 by Subscore	FAS
2.1.5.2	Summary of Total Symptom Scores for Dryness From Baseline to Week 12 for Female	FAS
2.1.6	Summary of PGIC Category at Weeks 4, 8, and 12	FAS
2.1.7	Summary of PROMIS Fatigue Short Form From Baseline to Week 12	FAS
2.1.8	Summary of FSFI From Baseline to Week 12 (Females Only)	FAS
2.1.9	Summary of EQ-5D From Baseline to Week 12	FAS
Safety		
3.1 Study Drug Exposure		
3.1.1	Summary of Drug Compliance	FAS
3.1.2	Summary of Study Drug Exposure	FAS

Table No.	Title	Population
3.2 Adverse Events		
3.2.1	Overall Summary of Treatment-Emergent Adverse Events	FAS
3.2.2	Summary of Treatment-Emergent Adverse Events by MedDRA System Organ Class and Preferred Term	FAS
3.2.3	Summary of Treatment-Emergent Adverse Events by MedDRA Preferred Term in Decreasing Order of Frequency	FAS
3.2.4	Summary of Treatment-Emergent Adverse Events by MedDRA System Organ Class, Preferred Term, and Maximum Severity	FAS
3.2.5	Summary of Grade 3 or Higher Treatment-Emergent Adverse Events by MedDRA System Organ Class and Preferred Term	FAS
3.2.6	Summary of Treatment-Related Adverse Events by MedDRA System Organ Class and Preferred Term	FAS
3.2.7	Summary of Treatment-Related Adverse Events by MedDRA Preferred Term in Decreasing Order of Frequency	FAS
3.2.8	Summary of Treatment-Related Adverse Events by MedDRA System Organ Class, Preferred Term, and Maximum Severity	FAS
3.2.9	Summary of Grade 3 or Higher Treatment-Related Treatment-Emergent Adverse Events by MedDRA Preferred Term	FAS
3.2.10	Summary of Treatment-Emergent Adverse Events Leading to Death by MedDRA System Organ Class and Preferred Term	FAS
3.2.11	Summary of Treatment-Emergent Serious Adverse Events by MedDRA System Organ Class and Preferred Term	FAS
3.2.12	Summary of Treatment-Emergent Serious Adverse Events by MedDRA Preferred Term in Decreasing Order of Frequency	FAS
3.2.13	Summary of Treatment-Related Serious Adverse Events by MedDRA System Organ Class and Preferred Term	FAS
3.2.14	Summary of Treatment-Emergent Adverse Events Leading to Dose Interruption by MedDRA System Organ Class and Preferred Term	FAS
3.2.15	Summary of Treatment-Emergent Adverse Events Leading to Discontinuation of Treatment by MedDRA System Organ Class and Preferred Term	FAS
3.2.16	Summary of Nonserious Treatment-Emergent Adverse Events by MedDRA System Organ Class and Preferred Term ^a	FAS
3.3 Laboratory		
3.3.1	Summary of Laboratory Values - Hematology	FAS
3.3.2	Summary of Laboratory Values - Chemistry	FAS
3.3.3	Shift Summary of Hematology Laboratory Values in CTC Grade - To the Worst Abnormal Value	FAS
3.3.4	Shift Summary of Chemistry Laboratory Values in CTC Grade - To the Worst Abnormal Value	FAS
3.4 Vital Signs		
3.4.1	Summary of Systolic Blood Pressure	FAS
3.4.2	Summary of Diastolic Blood Pressure	FAS
3.4.3	Summary of Pulse	FAS
3.4.4	Summary of Respiratory Rate	FAS
3.4.5	Summary of Body Temperature	FAS

Table No.	Title	Population
3.5 ECG		
3.5.1	Summary of PR Interval (msec) From 12-Lead ECG	FAS
3.5.2	Summary of RR Interval (msec) From 12-Lead ECG	FAS
3.5.3	Summary of QT Interval (msec) From 12-Lead ECG	FAS
3.5.4	Summary of QRS Interval (msec) From 12-Lead ECG	FAS
3.5.5	Summary of QTcB Interval (msec) From 12-Lead ECG	FAS
3.5.6	Summary of QTcF Interval (msec) From 12-Lead ECG	FAS
3.5.7	Summary of Heart Rate (bpm) From 12-Lead ECG	FAS
3.5.8	Summary of Outliers of QT, QTcB, and QTcF Interval Value (ms) From 12-Lead ECG	FAS
3.5.9	Summary of Clinically Significant ECG Abnormality	FAS

Listings

Listing No.	Title
Demographic and Baseline Characteristics	
2.1.1	Participant Enrollment and Disposition Status
2.1.2	Participant Inclusion and Exclusion Criteria Violations
2.2.1	Protocol Deviations
2.4.1	Demographic
2.4.2	Baseline Disease Characteristics
2.4.3	General Medical History
2.4.4	Prior and Concomitant Medications
2.4.5	Prior Medications for Sjögren's syndrome
2.5.1	Study Drug Compliance
Efficacy	
2.6.1	SGUS Score
2.6.2	Stimulated and unstimulated salivary flow
2.6.3	ESSDAI
2.6.4	ESSPRI
2.6.5	Symptom scores for dryness of eyes, mouth, and vagina
2.6.6	PGIC category
2.6.7	PROMIS Fatigue
2.6.8	FSFI
2.6.9	EQ-5D
Adverse Events and Exposure	
2.7.1	Study Drug Administration
2.7.2	Adverse Events
2.7.3	Serious Adverse Events
2.7.4	Grade 3 and Higher Adverse Events
2.7.5	Adverse Events Leading to Death
2.7.6	Treatment-Related Adverse Events
2.7.8	Adverse Events Leading to Dose Interruption
2.7.9	Adverse Events Leading to Discontinuation

Listing No.	Title
Laboratory Data	
2.8.1	Clinical Laboratory Values – Hematology
2.8.2	Clinical Laboratory Values – Serum Chemistry
2.8.3	Abnormal Clinical Laboratory Values – Hematology
2.8.4	Abnormal Clinical Laboratory Values – Serum Chemistry
Vital Signs	
2.9.1	Vital Signs
2.9.2	Abnormal Vital Sign Values
2.9.3	Alert Vital Sign Values
ECG	
2.10.1	12-Lead ECG Values
2.10.2	Abnormal 12-Lead ECG Values
2.10.3	Alert 12-Lead ECG Values
